- Maternal responsiveness to infant cues will be objectively assessed by video-coding of all feeding observations. After each visit, three trained coders who are unaware of the experimental conditions and hypotheses of the study will code videos using the NCAFS, a reliable and valid means of observing and rating mother-child interactions during a feeding session. The NCAFS is validated for use with mothers and their 0-1-year-old infants, can be applied to a breast or bottle-feeding episodes, and has been used during both lab- and home-based feeding observations. It contains 76 observable behaviors that are organized into six subscales; for the proposed research, we will

focus the Maternal Sensitivity to Infant Cues subscale. Reliability will be established prior to full coding of all videos. To this end, coders will code 10 common videos, and will double-code 10 additional videos. Inter-coder comparison of the 10 common videos will be used to establish inter-coder reliability. Intra-coder comparison of the 10 double-coded videos will be used to establish intra-coder reliability. Full coding will not commence until a Kappa > 0.80 is reached for all coders. The PI is certified in this coding system and has it previously.

- Maternal feeding style, including responsive and pressuring feeding, will also be subjectively assessed at study entry and completion using the Infant Feeding Style Questionnaire (IFSQ; see Appendix 4), which assesses maternal behaviors (e.g., control) and beliefs (e.g., concern about feeding) related to infant feeding. This scale has been validated in diverse samples of mothers with young infants and the PI has used this measure in previous research.
- Infant growth will be assessed during all home-based assessments by trained research assistants measuring infant weight and height in triplicate using a portable infant scale/infantometer (models 334 and 233; Seca, Hamburg, Germany). To minimize bias, infants will always be weighed and measured while only wearing a clean diaper and prior to the observed feeding. We will use the World Health Organization (WHO) Anthro software version 3.0.1 (http://www.who.int/childgrowth/en/) to calculate age-and sex-specific weight-for-length z-scores (WLZ) based on the WHO growth standards. We will also assess infant adiposity by infant skin-fold thickness and waist circumference using standard protocols.

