#### **Statistical Considerations**

Data Analysis. All quantitative analyses will be conducted using SAS v.9.4 (SAS Institute Inc., North Carolina, USA). Oualitative interview data will be transcribed and sorted into thematic categories using constant comparison within the framework of grounded theory. We will use linear regression to model the change in infant intake and maternal responsiveness (Aim 1) and change in WLZ, skinfolds, waist circumference (Aim 2) by the primary study variable of *clear* versus *opaque* group. For Aim 3, we will examine the feasibility, fidelity, adherence, acceptability, and safety of the intervention by summarizing quantitative and qualitative data related to recruitment and retention, mothers' use of their assigned bottles, perceptions of and barriers to using the bottles, and any issues related to infant inadequate weight gain or weight loss. We will then explore whether variations in intervention feasibility, fidelity, adherence, acceptability or safety are correlated with baseline characteristics of mothers (e.g., weight status, race/ethnicity, socioeconomic status, parity, feeding practices and styles, non-maternal caregiver involvement in feeding) and infants (e.g., sex, birth weight, weight status, temperament). Finally, we will assess whether the effects of the intervention on infant intake, maternal responsiveness, and infant WLZ change are moderated by the following factors: nipple type; mothers' adherence to the intervention, race/ethnicity, parity, or feeding practices and styles; infants' sex, temperament, and timing of solid food introduction; and the extent to which non-maternal caregivers are feeding the infant. Moderation will be explored by including a group by moderator interaction term in the linear regression models used to explore Aims 1 and 2. All inferential analyses will be preceded by appropriate descriptive statistics and graphs to determine that assumptions for linear regression are satisfied.

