**Power calculations.** The proposed sample size (n=100) was selected so that there will be adequate power to test for statistical significance for study aims. Because our previous research has shown <10% attrition after 12 weeks, we conservatively estimate 20% of participants will drop out and 120 mother-infant dyads will be recruited to account for this predicted attrition rate. For Aim 1, which examines the impact of bottle type on infant intake and maternal responsiveness, there is 80% power to detect a 19.1 mL difference in intake and 1.32 point difference in change of NCAFS score from baseline to 12-week follow-up between the *clear* and *opaque* groups, using  $\alpha = .05$ . For Aim 2, which examines the impact of bottle type on weight for length z-scores (WLZ), there is 80% power ( $\alpha = .05$ ) to detect a difference of 0.59 in change of WLZ from baseline to 12-week follow-up between the *clear* and *opaque* groups. Given rapid weight gain has been defined as z-score change  $\geq 0.67$  SD, a between-group difference in WLZ change of this magnitude (0.59 SD) would be clinically significant. Power calculations are based on a pilot study for which the between-subject standard deviation for infant intake was 33.7 mL and for the NCAFS scales is 1.91; this calculation also assumes that the mothers assigned to the *clear* group will have a higher correlation in scores between baseline and 12-week follow-up (r = .55), whereas mothers assigned to the *opaque* group will have a lower correlation in scores between baseline and 12-week follow-up (r =.40). The latter calculation assumes the standard deviation for WLZ is 1.0, and that the correlation between WLZs over 12-weeks for infants is  $r = .45^{.60}$ 

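### The NCAFS detectable difference of 1.32 points does not follow from the SD, correlations and sample size printed with it, which give about 1.11

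*Combined protocol and SAP*

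**What the plan says.** All the figures are in the Power calculations paragraph under Statistical Considerations.

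- Sample size: "The proposed sample size (n=100) was selected so that there will be adequate power". The paragraph also plans to recruit 120 dyads and allows for 20% dropout.
- Intake (Aim 1): "there is 80% power to detect a 19.1 mL difference in intake".
- Maternal responsiveness (Aim 1): in the same sentence, a "1.32 point difference in change of NCAFS score from baseline to 12-week follow-up", at alpha .05.
- WLZ (Aim 2): 80% power "to detect a difference of 0.59 in change of WLZ from baseline to 12-week follow-up", with an SD of 1.0 and a correlation of .45.
- Inputs for Aim 1: "the between-subject standard deviation for infant intake was 33.7 mL and for the NCAFS scales is 1.91". The clear group is given a correlation of .55, and the opaque group "will have a lower correlation in scores between baseline and 12-week follow-up (r =.40").

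The Data Analysis paragraph sets out the model: "We will use linear regression to model the change in infant intake and maternal responsiveness (Aim 1"), with bottle group as the explanatory variable. Under Measures, the NCAFS score of interest is narrowed to one of six subscales: the study will "focus the Maternal Sensitivity to Infant Cues subscale". Neither the allocation ratio nor the sidedness of the test is stated.

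**The concern.** A detectable difference is fixed once the SD, correlations, sample size, alpha and power are given. The two Aim 1 figures sit in one sentence and share their assumptions, yet they imply different precision. Dividing each by its SD gives 19.1/33.7 = 0.567 for intake and 1.32/1.91 = 0.691 for NCAFS, which is 22% higher. The printed correlations do not explain a gap of that size.

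This is the only power statement for maternal responsiveness, one of the two Aim 1 outcomes. As printed, a reader cannot tell whether the design has 80% power at 1.11 or at 1.32 points. If 1.32 is right, the printed SD or correlations are not the ones used. That matters for a pilot whose stated purpose includes judging whether the intervention can be scaled to larger trials, because its planning values may be reused.

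**Working it through.** **Inputs.** From Power calculations: NCAFS SD 1.91; r = .55 (clear) and .40 (opaque); WLZ SD 1.0 and r = .45; intake SD 33.7 mL; n = 100; alpha .05; power 80%. Assumed: 1:1 allocation (50 per arm) and a two-sided test. Regressing change on group alone is equivalent to a two-sample t-test on change.

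**Formulas.** Change SD = SD × √(2(1 − r)). With 50 per arm, noncentral t with 98 degrees of freedom, two-sided .05 and 80% power, the standardised detectable difference is 0.5659. The detectable difference is 0.5659 × SD, using the root-mean-square of the two arms' SDs where they differ.

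**Step 1: the neighbouring figures.**

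- WLZ: change SD = √(2 × .55) = 1.049; 0.5659 × 1.049 = 0.594 (0.588 by normal approximation). Printed: 0.59. It reproduces.
- Intake, without correlations: 0.5659 × 33.7 = 19.07 mL. Printed: 19.1. It reproduces as a difference in intake. As a difference in change with the printed correlations it would be 19.54 (19.35 by normal approximation).

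**Step 2: NCAFS.**

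- Clear: 1.91 × √(2 × .45) = 1.812.
- Opaque: 1.91 × √(2 × .60) = 2.092.
- Root-mean-square: √((1.812² + 2.092²)/2) = 1.957.
- Detectable difference: 0.5659 × 1.957 = **1.108** (1.097 by normal approximation). Printed: 1.32. Ratio: 1.32/1.108 = 1.19.
- Power at 1.32: standard error = √((1.812² + 2.092²)/50) = 0.391; noncentrality = 1.32/0.391 = 3.37; power = 91.6%. Simulation with Welch's test (40,000 runs) gave 91.3%.

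**Step 3: what would produce 1.32.**

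- Smaller arms: 35 per arm gives 1.330 and 36 gives 1.311. The same arms would make WLZ 0.713 and 0.702, and intake 22.9 and 22.6 mL without correlations.
- A larger change SD: 1.32/0.5659 = 2.33. That needs a raw SD of about 2.28 at the printed correlations, or an average r of about .25 at SD 1.91.

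**Step 4: unstated assumptions, one changed at a time** (t-based).

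| Change | NCAFS detectable difference |
|---|---|
| Baseline-adjusted, SD × √(1 − r²) | 0.95 |
| One-sided | 0.98 |
| Follow-up only, no correlations | 1.08 |
| 48 per arm (120 × 0.8 = 96) | 1.13 |
| r = .40 in both arms | 1.18 |
| 40 per arm (100 × 0.8 = 80) | 1.24 |
| 75:25 clear:opaque split | 1.32 |

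Only the 75:25 split reaches 1.32. It would make WLZ 0.685 and intake 22.0 mL, against the printed 0.59 and 19.1. Changing two at once, 40 per arm with r = .40 in both arms, gives 1.31 (normal) to 1.33 (t). It contradicts the printed r = .55 and makes WLZ 0.66 to 0.67.

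**Step 5: a check that needs no allocation or sidedness.** If one test on change and one n serve both outcomes, the ratio of the NCAFS to the WLZ figure depends only on the change SDs and the split between arms. At 1:1 it is 1.957/1.049 = 1.87. Under any split it cannot exceed 2.092/1.049 = 1.99. The printed ratio is 1.32/0.59 = 2.24, or 2.21 at the most favourable rounding (1.315/0.595).

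**The case against.** The strongest objection is that the recalculation rests on assumptions the plan does not print. Allocation is one: the Randomization paragraph says only that the scheme is computer-generated, and a 75:25 split does return 1.32. The analysed n is also unsettled, because 120 recruited less 20% leaves 96, while 100 enrolled less 20% leaves 80. These points stand as gaps in reporting, but they do not rescue the figure. The 75:25 split and the smaller arms that reach 1.32 move WLZ and intake well away from their printed values, and 48 or 40 per arm gives only 1.13 or 1.24. The ratio check in Step 5 excludes every split if the two change outcomes share one test and one n.

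It can also be said that intake reproduces closely only when the correlations are dropped, so the two Aim 1 figures may not share one method. That is fair. However, choosing between a change and a follow-up analysis moves the result by about 2.5% (19.54/19.07), not 19%.

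Lastly, the discrepancy is conservative, the study is a pilot, no clinically important NCAFS difference is stated, and n = 100 is not shown to derive from 1.32. All of this is true. It makes the point a correction to reporting, not a threat to the design. It does not make the printed power statement correct.

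**Conclusion.** The point holds. With 50 dyads per arm, a two-sided .05 test of change, SD 1.91 and correlations of .55 and .40, the difference detectable with 80% power is 1.11 points. The printed 1.32 is 19% too large for those inputs; power at 1.32 is about 92%. Equal allocation and two-sidedness are assumptions, supported by their reproducing the WLZ figure, and the intake figure when read as a difference in intake. The alternatives examined that bring NCAFS to 1.32 conflict with a printed input or with those neighbouring figures.

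The documents do not reveal whether 1.32 is wrong or whether the SD, the correlations or the n behind it were different. If the printed inputs are right, the trial is better powered for 1.32 than claimed and needs no more participants. If 1.32 is right, at least one printed input needs correcting.

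**What to change.** Reconcile the NCAFS sentence in Power calculations in one of two ways.

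1. If the printed inputs stand, restate it along these lines: *with 50 dyads per arm analysed, a two-sided two-sample t-test on change at alpha .05, SD 1.91 and correlations of .55 (clear) and .40 (opaque), a 1.11-point difference in NCAFS change is detectable with 80% power.* If the analysed number is to be 96 dyads, the figure is 1.13; if 80, it is 1.24.
2. If 1.32 is intended, print the SD, correlations and analysed n that produce it.

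In either case, state the allocation ratio and sidedness, and say whether the SD of 1.91 belongs to the Maternal Sensitivity to Infant Cues subscale or to another NCAFS score; the power paragraph refers only to the scales in general. As a separate matter of wording, say whether 19.1 mL is a difference in intake or in change of intake, since Data Analysis models change (about 19.4 to 19.5 mL with the printed correlations).

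The cost is an edit to one paragraph. The sample size and design stay as they are.

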#### Potential Risks and Plan for Data Safety and Monitoring

**Potential Risks.** The risk involved in this study is considered minimal. Some infants or mothers may dislike using the bottles we offer during the infant-feeding study, thus may perceive the experience of using these bottles as unpleasant. It is also possible that an unintended consequence of the opaque bottles will be that mothers and caregivers underfeed their infants, resulting in inadequate growth for their infants. Some mothers may feel uncomfortable answering questions about their attitudes about and concern for their infants' feeding and weight gain patterns. Additionally, some dyads may experience discomfort related to having their feedings video-recorded or having our research staff present in their homes. There is also risk of breach of confidentiality given that video records are being collected.

**Plan for Data Safety and Monitoring.** We have developed effective procedures for protecting participants' safety and confidentiality. All participants will be assured that they have the right to opt out of any part of the study with which they feel uncomfortable. Additionally, we will check-in with mothers and infants frequently to monitor infants for insufficient growth (<20-30g/day) or weight loss. The research assistants will monitor the participants for adverse events, including inadequate infant growth.

The PI will hold primary responsibility for ensuring that the proposed trial is conducted according to protocol and carrying out the above data safety and monitoring plan. However, the PI will also identify a local pediatrician to serve as the Data and Safety Monitor (DSM) for the proposed study. Given that feeding interactions and infant growth are of primary interest, we will identify a local pediatrician with particular expertise in this area and have several pediatricians affiliated with our research center who have this expertise. Once appointed, the DSM will help ensure that our protocol and intervention and assessment of adverse events are in line with local pediatric providers' usual care plans. The DSM will meet with the PI and Co-I's quarterly to review and evaluate the accumulated study data for participant safety, study conduct and progress, and alignment with pediatric providers' usual care plans. The DSM will also ensure that all enrolled families have a pediatrician with whom they regularly consult to add an additional layer of monitoring and protection.

Infants who exhibit slower than expected growth will be referred to their pediatrician or emergency services for further consultation and will be removed from the study if the PI and/or DSM deem study participation harmful to the infant or family.

We will also employ strategies we have used in previous studies to minimize discomfort, including having familiar research staff present in the homes during assessments, and moving to another room or outside the home (if another room is not available) during video-recorded feeding interactions. The PI has significant expertise in coding video-recorded feeding interactions and ensuring mother and infant comfort and confidentiality during this process. Furthermore, all research assistants will be trained to ensure that assessments are conducted in a professional and nonjudgmental manner.

Adverse events determined by the PI to be unanticipated problems involving risks to subjects or to others will be reported by the PI to the IRB within 10 days. Adverse events that are reviewed by the PI and not determined to be unanticipated problems involving

risks to subjects or to others will be reported per IRB policy at the time of continuing review.

All study personnel will be informed by the PI about any unanticipated problems involving risks to subjects or to others. If any protocol changes are needed, the PI will submit a modification request to the IRB. Protocol changes will not be implemented prior to the IRB approval unless necessary to eliminate apparent immediate hazards to the research participants. In such a case, the IRB will be promptly notified of the change following implementation (within 10 working days). Protocol adherence will be monitored by the PI during bi-monthly meetings with the research assistants. If the PI is made aware of an unanticipated protocol deviation, the PI will report this deviation to the IRB within 10 days.

To protect participant confidentiality, all participant data will be treated as confidential. Our research team has significant expertise in maintaining data integrity and confidentiality in studies involved video records and clinical trials and will employ that expertise in the present study. Specifically, participants will be informed of this potential for breach of confidentiality, video files will be immediately downloaded to secure servers at respective sites and deleted from video cameras immediately. Records will be safeguarded according to the policies of HIPAA, our IRB, and the applicable state laws governing the conduct of the studies, which promote the protection of confidential health information.

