#### **METHODS:**

#### **Design and Sample**

Design. We have designed a 12-week randomized clinical trial to explore the efficacy

and feasibility of a 12-week opaque, weighted bottle intervention. Previous research suggests that, during early infancy, 12 weeks is a sufficient duration of follow-up to capture divergences in growth trajectories related to feeding mode, and that the window between 12-24 weeks is when associations between feeding mode and excess weight gain emerge. Mother-infant dyads will be randomized to use conventional, clear bottles (*clear* group) or opaque, weighted bottles (*opaque* group). Dyads will participate in home-based assessments of bottle-feeding interactions at study entry and 12 weeks, with brief assessments at 2 and 6 weeks.

**Subjects and Recruitment.** A total of 100 mother-infant dyads will participate. We will use recruitment methods similar to those effectively used in our previous research. Mothers will be recruited through ads in local newspapers; targeted social media ads; Women, Infant & Children (WIC) offices; OB/GYN and pediatrician offices; mass mailings; online sites; and a list of past participants who have asked to be notified of future studies. See **Appendix 1** for example recruitment materials.

Given San Luis Obispo and Santa Barbara Counties are predominately White and Hispanic (66% White, 35% Hispanic, 2% Black, and 4% Asian), we will over-sample Black mothers to increase sample diversity (targets: 55% White, 35% Hispanic, 13% Black, 4% Asian). Both English and Spanish-speaking mothers and their healthy, term infants of either sex will be eligible.

Inclusion criteria for the dyads include:

- 1) mothers 18-40-years of age
- 2) infants <8-weeks of age
- 3) mother is planning to bottle-feed, or is currently bottle-feeding, her infant
- 4) mother predominantly or solely responsible for infant feeding
- 5) dyad has a pediatrician and plans to attend infant well-visits
- 6) mother is willing to use stainless-steel bottles and to provide the study will her current bottles, which would be returned after study completion
- 7) prior to the introduction of solid foods

To protect infants who might be at risk for underfeeding or inadequate growth, exclusion criteria for infants include known risk factors:

- 1) preterm birth (i.e., gestational age <37 weeks)
- 2) low birth weight (<2500 g)
- 3) maternal smoking during pregnancy

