#### **Experimental Conditions**

- 1. Control Group: Conventional, Clear Bottles: These mothers will receive usual care from their pediatric providers and each mother will be given 12 conventional, clear bottles of various sizes (4-12 ounces) that are compatible with a variety of different nipples manufactured by leading bottle companies. Mothers will also be given a handout about paced bottle-feeding (see Appendix 3), which includes messages about feeding in response to infant cues.
- 2. Intervention Group: Opaque Bottles: These mothers will receive everything provided to the *clear* group, but will instead receive 12 opaque, weighted bottles of various sizes (4-12 ounces). These bottles will be stainless steel (Pura Kiki, California, USA) and compatible with a variety of different nipples manufactured by leading bottle companies. These bottles weigh ~70g more than comparable plastic bottles, which is similar to the amount of added weight used in our pilot work. Mothers in the intervention group will also receive a handout about how opaque bottles can help them attend to infant cues.

For both groups, we will replace *all* of the mother's current bottles with study bottles and will ensure that the study bottles match the size of the bottles the mother currently uses; we will also supply any additional bottles needed for infant care in other settings (e.g., child care). Mothers will be asked to use the study bottles for all bottle feedings, regardless of whether the mother or another caregiver is feeding the infant. Monthly phone calls from the study interventionist will query about any need to replace bottles or any feeding difficulties; we will also instruct the mother to contact us if she needs more bottles. We anticipate that the features of allowing mothers to continue using their preferred nipple and replacing all of the mothers' bottles with study bottles will encourage compliance.

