#### **Assessments and Measures**

As illustrated in the **Table**, we will conduct two assessments (separated by one day) at both study entry and completion to objectively measure infant intake and maternal responsiveness. Two brief visits will occur at weeks 2 and 6 to assess infant growth and maternal adherence to the intervention. All assessments will be administered by blinded research assistants.

Study Week:	1	1	2	6	12	12
Assessment Type:	Pre- Test 1*	Pre-Test 2*	Brief visit for	Brief visit for	Post-Test 1*	Post- Test 2*
Bottle used during observation: Clear Bottle Group	Clear	Opaque	growth check	check	Opaque	Clear
Opaque Bottle Group	Opaque	Clear			Clear	Opaque

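### No study weight is scheduled between weeks 6 and 12, so the study cannot check its own g/day growth criterion during the second half of the intervention

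*Combined protocol and SAP*

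**What the plan says.** Under Potential Risks and Plan for Data Safety and Monitoring, the protocol accepts that caregivers using opaque bottles might underfeed and that growth might suffer. The safeguard is: "we will check-in with mothers and infants frequently to monitor infants for insufficient growth", where insufficient means below 20-30 g/day, and also for loss of weight. No interval is attached to the word frequently. The same section has research assistants watch for adverse events, including poor growth, and adds: "The DSM will meet with the PI and Co-I's quarterly to review and evaluate the accumulated study data for participant safety".

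The schedule is set elsewhere. Design and Sample gives the duration ("We have designed a 12-week randomized clinical trial to explore the efficacy") and the visits: "Dyads will participate in home-based assessments of bottle-feeding interactions at study entry and 12 weeks, with brief assessments at 2 and 6 weeks". Assessments and Measures adds: "Two brief visits will occur at weeks 2 and 6 to assess infant growth and maternal adherence to the intervention". The infant growth item under Measures says that growth "will be assessed during all home-based assessments by trained research assistants measuring infant weight and height in triplicate".

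Between visits, Experimental Conditions provides for calls in both groups: "Monthly phone calls from the study interventionist will query about any need to replace bottles or any feeding difficulties". To enter, a dyad must have a pediatrician and intend to go to well-visits. The safety plan sends slow-growing infants for outside medical review and lets either the investigator or the DSM decide on removal.

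**The concern.** The safety plan and the visit schedule describe different intensities of monitoring. The criterion is a rate, so a check-in without a weight cannot evaluate it. Weights are spaced more widely as the intervention goes on, and the longest gap comes last.

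The harm is one the protocol takes seriously. It reports 26% lower intake with opaque bottles in its laboratory trial, and it excludes infants with known risk factors for underfeeding or inadequate growth. If growth slows only after week 6, the study's own measurements will first show it at the week-12 visit, when the intervention is ending. Someone reading the safety plan alone would expect closer surveillance than the schedule delivers.

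**Working it through.** The plan states no figure to reproduce. The check sets the criterion against the schedule.

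1. **Inputs.** Study weights at weeks 1, 2, 6 and 12 (Design and Sample; Assessments and Measures and its Table). Intervention length 12 weeks = 84 days (Design and Sample). Criterion below 20-30 g/day (safety plan). Calls monthly (Experimental Conditions).

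2. **Gaps between study weights.** Gap in days = difference in weeks × 7.
   - Weeks 1 to 2: 1 × 7 = 7 days.
   - Weeks 2 to 6: 4 × 7 = 28 days.
   - Weeks 6 to 12: 6 × 7 = 42 days.

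3. **Share of the intervention in the last gap.** 42/84 = 50%. Counting only from the week-1 visit, 7 + 28 + 42 = 77 days, and 42/77 = 55%.

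4. **When the criterion can be evaluated.** A rate becomes available at the second weight of each pair, that is at weeks 2, 6 and 12. Only the first two fall while a substantial part of the intervention remains.

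5. **Growth that passes unchecked.** At the criterion's own limits, gain over the last gap would be 42 × 20 = 840 g to 42 × 30 = 1,260 g. No study weight tests this until week 12.

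6. **The range.** The two ends differ by 42 × (30 − 20) = 420 g over that gap. This is the width of the criterion, not an estimated deficit. An infant gaining 25 g/day (an illustrative value) would meet the criterion for insufficient growth at the upper end and not at the lower, and the text does not say how the range is applied.

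7. **Other contact in the gap.** Monthly calls: 42/30.4 = 1.4, so about one call. Its stated content is bottle replacement and feeding difficulties. Pediatric care continues, but the text gives no well-visit timing and no route for those weights to reach the study.

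**The case against.** The strongest reply is that a check-in need not be a weighing and that several layers remain after week 6: the call, research assistants alert to adverse events, and a pediatrician for every family. This has force. A pediatrician who sees poor growth can act without telling the study, and a mother can report a feeding difficulty by telephone. What it does not supply is a value for the g/day criterion. A mother who underfeeds without knowing it has no difficulty to report. The intake tracker does not fill the gap either: it stores data, is still under development, and no safety review of its data during the trial is described. The appendices are not available here, so a weight question could exist in a form that the main text does not mention.

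A reader might infer three stronger points, which the documents do not support.

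- *That underfeeding after week 6 cannot trigger action in time.* The layers above can trigger action. Only the study's own weights are absent, and infants may be weighed elsewhere.
- *That action must wait for the quarterly DSM meeting.* Assuming meetings 13 weeks apart and enrolment at random relative to them, a meeting falls within weeks 6-12 for 6/13 = 46% of infants. That is not a time to action: the safety plan ties referral to slow growth itself, and the investigator may remove an infant without the DSM.
- *That the Aim 3 safety conclusion rests on the first half only.* Week-12 weights are taken, and the Data Analysis section includes problems with weight gain or weight loss in the Aim 3 summary, so gain over weeks 6-12 can be counted there.

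**Conclusion.** The concern holds as a gap in detection during exposure. For 42 of 84 days the study has no means in its main text of evaluating the growth criterion that it promises to monitor frequently, and the criterion is itself an unresolved range. The gap does not affect the Aim 2 comparison or prevent a safety summary after follow-up, and it does not show that a harmed infant would go unnoticed.

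The conclusion rests on reading the schedule as complete, with no study weights beyond weeks 1, 2, 6 and 12, and on the calls covering only what is stated. The documents do not allow an estimate of how many infants would slow after week 6. The change is worth making because it is cheap and bears on a harm that the protocol itself names.

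**What to change.** 1. Reconcile the promise of frequent monitoring and the 20-30 g/day range in the safety plan with the weighing schedule in Design and Sample and in Assessments and Measures, so that a reader can tell when and from which weights the criterion is evaluated.
2. Add to the existing monthly call, in both groups, a question recording the infant's most recent clinic weight and its date. Use the answer for safety only and keep it out of the Aim 2 outcome.
3. Ask the sponsor and the DSM to reconcile the quarterly DSM review with the DSM's role in individual removal decisions.

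No threshold, visit interval or escalation rule is proposed here; those are for the sponsor and the DSM.

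The cost is one question with two data fields in a call already planned. There are two drawbacks. Clinic scales differ from the study scale, so a rate that combines the two carries extra error. And the protocol gives no well-visit dates while admitting infants of any age under 8 weeks, so a clinic weight may not fall in weeks 6-12 for every infant. The question narrows the gap but may not close it.
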